8. STUDY POPULATION

All study subjects will be enrolled from the normal surgical cataract population at up to 10 sites in the USA. Up to 241 subjects will be enrolled to achieve approximately 230 randomized and contralaterally-operated subjects to ensure approximately 200 evaluable subjects at 3 months. Each site should implant a minimum of 20 subjects, and no site may implant more than 25% of the enrollment total.

This study will include only subjects undergoing bilateral, primary, cataract extraction and IOL implantation and who meet all of the study inclusion and exclusion criteria in both eyes. All subjects who meet the inclusion/exclusion criteria will be offered enrollment in the study. Eligibility criteria may not be waived by the investigator. Any questions regarding patient eligibility are to be discussed with AMO prior to subject enrollment. Those subjects who meet the inclusion/exclusion criteria and agree to participate will be randomly assigned to receive the investigational OVD in one eye and

the currently-available, control OVD in the fellow eye. Subjects will be enrolled at each site sequentially until the recruitment goals are met or the site limit is reached.

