20.1 ANALYSIS POPULATION

For the primary endpoints of cumulative IOP rate and mean percent ECC change, the primary analysis population will be an Intent-to-Treat (ITT) population. The ITT population will include all subjects who were randomized and had surgeries using a test OVD in one eye and a control OVD in the other eye. For randomized subjects who received study OVDs but did not have data available at a specific postoperative visit

(i.e., missing postoperative data), data imputation will be performed using MCMC multiple imputation techniques¹. Per-protocol and sensitivity analyses (e.g., worst-case, best-case and tipping-point analysis) will also be provided for the primary IOP and ECC endpoints. Sensitivity analyses will include all randomized subjects whether a study OVD was used or not. The safety population (SP) will include available subjects who had one or both study OVDs with available data at the time of analysis (i.e., no data imputation). Only the safety population will be used for analyses of secondary safety endpoints and other endpoints. For the secondary safety endpoints, no multiplicity or imputation will be done since they are considered safety endpoints and are not intended for claims. Only safety population (SP) will be used for the secondary safety endpoints.

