2 ANALYSIS POPULATIONS

2.1 ANALYSIS POPULATIONS/HANDLING OF MISSING DATA

Four different populations will be presented for the primary endpoints (cumulative IOP spike, and mean percent ECC change): Intent-to-Treat (ITT), sensitivity analysis, safety population, and per-protocol population. The ITT population will be the primary analysis population for the primary endpoints and will include all subjects who were randomized and had surgeries using the test OVD in one eye and the control OVD in the other eye (i.e., paired OVDs were used). Sensitivity analysis will include all subjects who were randomized regardless of OVD use; i.e., include subject that had no study OVD, one study OVD or paired OVDs used. The safety population will include available subjects who had one or both study OVDs. The per-protocol population will include available subjects who had surgeries with paired OVDs, were evaluated within the proper study interval and were without clinically-relevant protocol deviations

For the secondary safety endpoints and other additional study endpoints, only data from the safety population will be presented.

INTENT-TO-TREAT ANALYSIS

The ITT population will include all subjects who were randomized and had surgeries using a test OVD in one eye and a control OVD in the other eye (i.e., paired OVDs). For randomized subjects who had study OVDs but did not have data available at a specific postoperative visit, (e.g. they missed a visit, were lost to follow-up), data will be imputed for the ITT analyses using a planned multiple imputation method. The planned imputation method is the MCMC full-data imputation as described in Little & Rubin¹. Data imputation and analysis will be performed using the MI and MIANALYZE procedures² in SAS®.

SENSITIVITY ANALYSIS

Sensitivity analysis will include all subjects who were randomized whether they had none, one OVD or both OVDs. For missing data in the sensitivity analysis, different imputation approaches (e.g. worst-case scenario, best-case scenario and tipping point) will be used. For the difference between eyes, a worst-case scenario will be performed with the worst difference score (that favoring the control the most) assigned to the missing data. For the best-case scenario, the difference score favoring the control OVD the most will be assigned to missing data. If more than 10 percent of randomized subjects have missing data at the primary analysis time point then a tipping point analysis will also be performed.

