8 SAMPLE SIZE CALCULATIONS

Cumulative IOP spikes are defined as an IOP of 30 mm Hg or greater at any visit. The percentage of eyes with IOP spikes will be assumed to be 30% (15798:2001(E), Annex D), and a correlation of 0.5 (medium strength). Using a one-sided, McNemar test and assuming an alpha of 0.025, power = 0.80, and a minimum detectable difference of $\delta=0.10$ yields a sample size of $n=195$ eyes per group. Adding 20% for lost-to-follow-up and screen failures yields a sample size of 241 subjects (482 eyes total with contralateral control).

Assuming a 1-sided, non-inferiority, paired t-test with $\alpha=0.025$, a common standard deviation of 305 cells⁵, and a correlation of 0.50 (medium strength), a sample of $n=195$ subjects (390 eyes) provides over 99% power to detect a minimum clinically significant decrease in mean Endothelial Cell Count (ECC) of at least $\delta =125$ cells. This corresponds to a 5% decrease using a standard deviation of 12% from a baseline ECC of 2500 cells.

Since the sample size required to detect a minimum clinically significant effect for IOP spikes also provides over 99% power to detect a minimum clinically significant effect for ECC loss, the sample size for the study will be based on the number calculated for IOP spikes. Therefore, the sample size required is 195 subjects. Adding 20% for lost-to-follow-up and screen failures yields a sample size of 241 subjects (482 eyes).

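### SAP 2.1 runs the tipping-point analysis only above 10% missing, which leaves about 4% to 10% missing without a graded check on the IOP endpoint, and its worst- and best-case rules need correcting

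*SAP*

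**What the plan says.** Protocol 20.1 states that "Per-protocol and sensitivity analyses (e.g., worst-case, best-case and tipping-point analysis) will also be provided for the primary IOP and ECC endpoints". The Data Analysis part of the protocol synopsis gives the same list. Neither sets a threshold, although the list is given by way of example.

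SAP 2.1 names the same three analyses but makes one of them conditional: "If more than 10 percent of randomized subjects have missing data at the primary analysis time point then a tipping point analysis" is called for. Protocol 20 and the time-frame note in SAP Appendix I make 3 months the key time point. The IOP endpoint, as defined in SAP 8, is a reading of 30 mmHg or more at any visit.

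For the extremes, SAP 2.1 says that "a worst-case scenario will be performed with the worst difference score (that favoring the control the most) assigned to the missing data". Its rule for the opposite extreme reads: "For the best-case scenario, the difference score favoring the control OVD the most will be assigned to missing data". On who is included: "Sensitivity analysis will include all subjects who were randomized whether they had none, one OVD or both OVDs". Protocol 20.1 agrees on that set.

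The primary analysis is ITT in subjects who had paired OVDs, with MCMC multiple imputation.

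**The concern.** Multiple imputation rests on an assumption about the missing values that the data cannot test. The sensitivity analyses exist to show how far that assumption can bend before non-inferiority is lost. A tipping-point analysis answers this by degree; a worst case answers only yes or no, at the most extreme setting.

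Four features of SAP 2.1 weaken this:

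- The 10% trigger equals the 10-point IOP margin. Each missing pair scored at the extreme moves the estimate by 1/N, so 10% missing can use up the whole margin before any allowance for sampling error.
- The trigger looks at 3 months, whereas the spike endpoint draws on five postoperative visits. A subject who attends at 3 months but lacks the 6-hour reading does not count. A subject seen at every early visit but absent at 3 months does.
- The worst score is given to the between-eye difference. For IOP this is control minus test, so the worst score of -1 requires a control eye that never spiked. If the control eye has already spiked, -1 is impossible. Surgeries are 14 to 45 days apart (Protocol 10.2), so half-observed pairs are foreseeable.
- Best and worst case both favor the control, so they do not bracket the result.

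At stake is what the trial can report about robustness when missingness is modest.

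**Working it through.** **Inputs.** From SAP 8: spike rate 30%, between-eye correlation 0.5, ECC SD 12%. From SAP 5.1 and 5.2: margins of 10 points (IOP) and 5% (ECC), one-sided alpha 0.025. From Protocol 8: "Up to 241 subjects will be enrolled to achieve approximately 230 randomized and contralaterally-operated subjects to ensure approximately 200 evaluable subjects at 3 months". Assumed: no observed IOP difference.

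**The plan's own figures.** With both rates at 30%, the discordant share is 2 × 0.3 × 0.7 × (1 − 0.5) = 0.21. The paired non-inferiority formula gives n = (1.960 + 0.842)² × 0.21 / 0.10² = 165. For 0.30 against 0.40 the share is 0.70 − 2 × (0.12 + 0.5 × √(0.21 × 0.24)) = 0.2355, and the McNemar formula gives 183 uncorrected or 202 with a continuity correction. The plan's 195 lies within this range, though I do not match it exactly. Nothing below depends on it.

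**Planned loss.** 30/230 = 13.0%; 41/241 = 17.0%. Both exceed 10%, so the SAP's condition is met.

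**IOP with complete data, 230 pairs.** SE = √(0.21/230) = 0.0302; half-width 1.96 × 0.0302 = 5.9 points; room to the margin 10 − 5.9 = 4.1 points.

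**IOP worst case.** With m of N pairs set to −1 and f = m/N, the estimate is −f, and the SE is √{[0.21(1 − f) + f − f²]/N}.

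| m of 230 | Missing | Estimate (points) | Lower limit (points) | Tipping point required? |
|---|---|---|---|---|
| 8 | 3.5% | -3.5 | -9.8 (passes) | No |
| 9 | 3.9% | -3.9 | -10.2 (fails) | No |
| 23 | 10.0% | -10.0 | -16.8 (fails) | No |
| 30 | 13.0% | -13.0 | -20.1 (fails) | Yes |

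With 241 as the base, failure starts at 10 pairs (4.1%, lower limit -10.3). In simulation with truly equal rates and 230 pairs, the worst case passes about 41% of the time with 10 missing, under 1% with 23 and under 0.1% with 30.

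**What a tipping point would add.** Let the missing pairs average d, take their mean square as the larger of 0.21 and |d|, and find where the lower limit reaches -10. This ignores between-imputation variance, so the true tipping point comes somewhat sooner. With no observed difference:

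- 23/230 missing: the missing pairs must average about 39 points more spikes in test eyes. Check: estimate −0.1 × 0.386 = −0.0386; variance (0.9 × 0.21 + 0.1 × 0.386 − 0.0386²)/230 = 0.000983; lower limit −0.0386 − 1.96 × 0.0314 = −0.100.
- 30/230 missing: about 30 points.

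The worst case fixes this figure at 100 points. At 23 missing, if the observed difference were -2 or -3 points (an assumption), tipping would fall to about 23 or 14 points. A reader would judge 39 and 14 very differently, yet the worst case fails in both.

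**ECC.** At correlation 0.5 the SD of the paired difference is √(2 × 12² × 0.5) = 12%. I read the worst score as the worst observed difference, about -33% in some 200 pairs. In simulation with equal products and 230 pairs, the worst case passes about 98% of the time with 10 missing, 40% with 23 and 12% with 30. With 30 missing, an assumed SD of 8% gives about 84%, and 16% gives under 1%.

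**The case against.** The strongest objection is that the plan already covers the case it expects. A reader might infer that missing data go untested at the planned loss because the worst case is then hopeless. The documents do not support that: 13% to 17% exceeds the SAP's own trigger, so the tipping point runs exactly there, and deleting the condition changes nothing at that level. This stands and confines the point to 10% missing or less.

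A reader might also infer that the worst case is bound to fail on both endpoints. It is near-certain for IOP only, and only if every subject lost by 3 months is scored -1. Spikes count at any visit, so many such subjects would be partly observed, and the 13% figure is an upper bound for this endpoint. For ECC the result turns on the SD.

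The protocol introduces its list as examples, so the SAP's threshold departs from the protocol without breaking an absolute commitment. A worst case is meant as a bound, and failing it is no design error; success rests on the ITT analysis. In the 4% to 10% band it would still be reported and would signal fragility. All this is fair, but it would give the same signal whether the missing pairs had to differ by 14 points or by 39.

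Nor does the SAP say that observed eyes are overwritten. It assigns the score to missing data and is silent on half-observed pairs. That is a gap in the rule, which a literal reading would fill wrongly.

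Finally, one might want to drop randomized subjects who had no OVD from the sensitivity set. Both documents include them, and this is the only analysis that covers everyone randomized.

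**Conclusion.** The concern holds in a limited form. SAP 2.1 adds a 10% threshold that the protocol lacks and that is tied to the 3-month visit although the IOP endpoint counts a spike at any visit. The consequence is a gap from about 4% to 10% missing (9 to 23 of 230 pairs), where the IOP worst case fails at zero observed difference and no graded analysis is required. This rests on the plan's 30% rate and 0.5 correlation, 230 pairs, and every missing pair scored -1. It does not extend to the planned loss, and for ECC it depends on the SD.

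Separately, the best case as written points the same way as the worst case, which is a plain error, and the worst-case rule does not say that observed eyes constrain it. None of this alters the primary test. It alters what the trial can say about robustness if follow-up is better than planned. The change should be made, but it is modest.

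**What to change.** In SAP 2.1:

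1. Delete the 10% condition. Run the tipping-point analysis (delta-adjusted imputation) at any level of missingness for both primary endpoints. This also removes the mismatch between a 3-month trigger and an any-visit endpoint.
2. Apply worst and best case to the missing eye data rather than to the between-eye difference, and keep an observed spike in either eye as a spike. A pair whose control eye has spiked and whose test eye is missing then scores 0 at worst, not -1.
3. Redefine the best case so that missing data favor the test OVD.
4. Keep the all-randomized sensitivity set, as both documents state.

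The cost is SAP wording and one extra analysis. It needs no new data, and because the protocol already names the analysis without a threshold, this brings the SAP into line with it.

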2.2 VISIT WINDOWS

Subject visits will occur at Preoperative (both eyes), Operative, 6 hour, 1 day and 1 week for each eye, and 1 month and 3 months for both eyes together. The exact number of days for each interval is described in the protocol. The number of eyes with missing visits or data outside of the visit interval will be reported.

2.3 DATA CONVENTIONS

Descriptive statistics will typically include sample size (N), mean, standard deviation (SD), median, minimum (Min.), and maximum (Max.) as appropriate for continuous variables. For categorical data, the frequency and proportion will be computed.

For continuous variables, statistical tests assuming normality will generally be used. However the data will be reviewed to evaluate whether the normality assumption is appropriate. If it is found not to be appropriate, either an appropriate transformation of the data (i.e., logarithmic) may be used or the corresponding non-parametric tests may be used. Deviations from the proposed statistical guidelines will be substantiated by sound statistical rationale. In this study, unless otherwise indicated, paired t-tests will be used for continuous data, Wilcoxon signed-rank test for ordinal data and McNemar's test for dichotomous data.

Unless otherwise indicated, alpha will be set to 0.05 for two-sided statistical testing with alpha set to 0.025 for one-sided testing.

2.4 RANDOMIZATION

Randomization will be done for each investigational site according to a centralized electronic randomization system. Once the surgeon has determined that the subject has met all specific criteria and selected which will be the first operative eye for a given subject, the randomization can occur indicating which OVD is to be used in the first eye surgery and the alternate OVD is to be used in the fellow eye surgery.

If mis-randomization occurs in the study, the subject's study data will be analyzed according to the randomization schedule in the ITT and sensitivity populations and will be analyzed according to the OVDs received in the safety population. The subject will be excluded in the Per-Protocol population analysis.

2.5 MULTIPLICITY ADJUSTMENT

No multiplicity adjustment is planned for the primary endpoints since both endpoints are required to meet statistical significance. No multiplicity adjustment is planned for the secondary safety endpoints as these are safety endpoints not intended for claims. Please see Section 6 for more details regarding the planned analysis of secondary safety endpoints.

2.6 SITE DIFFERENCES

For the primary endpoints, data will be reported by site using the safety population. To evaluate site differences, a mixed model analysis will be performed taking paired eyes into account. The model will include OVD group as a fixed variable with site and site by OVD group interaction as random variables. If the interaction term is significant at the 0.15 level, then further examination of effects of site will be evaluated. Baseline demographic data will also be reported by site.

3 ACCOUNTABILITY/DEMOGRAPHICS

3.1 ACCOUNTABILITY

The number of enrolled subjects will be tabulated by site. Subject accountability will be summarized as a frequency distribution by scheduled visits. A frequency table will be generated, showing the number of available eyes (those in interval and outside of the interval) and the number of missing and active subjects.

3.2 DEMOGRAPHICS

Subject demographic data including age, sex, race, ethnicity and eye color will be presented. Age will be determined at the time of the preoperative visit and will be categorized by less than 60, 60 to 69, 70 to 79, and equal to or older than 80 years old. In addition, age will be summarized with descriptive statistics. The frequency distributions of sex, race, ethnicity and iris color will also be tabulated.

4 PREOPERATIVE/OPERATIVE VARIABLES

Preoperative and operative variables will be reported for each OVD group. The frequency and proportion of eyes with selected responses will be tabulated for categorical data. Descriptive statistics will be used for continuous data. Statistical comparisons between OVD groups will be performed using paired analyses as appropriate (e.g., paired t-tests for continuous data; Wilcoxon signed-rank test for ordinal data; McNemar's test for paired binary proportions). Two-sided testing with an alpha level of 0.05 will be used for preoperative and operative variables.

5 POSTOPERATIVE PRIMARY ENDPOINTS

5.1 SAFETY: CUMULATIVE RATE OF IOP SPIKES 30 MMHG OR GREATER MEASURED POSTOPERATIVELY

The cumulative frequency and proportion of eyes with an IOP spike will be reported for both OVD groups for the safety population, PP population and sensitivity analysis. For ITT population (with imputation), only the difference between the OVD groups will be reported. The difference in the cumulative IOP spike rate will be analyzed by the McNemar test using a GLIMMIX procedure taking into account the paired data. The GLIMMIX model will model spike as the dependent variable and OVD group as an independent variable and include the SUBJECT = option for the paired eye data. The

hypothesis testing of non-inferiority for cumulative percentage of IOP spikes will be tested using a 1-sided, McNemar test at an alpha of 0.025 with a delta of 0.10 (10%). The null hypothesis is that the paired difference between eyes is less than or equal to -10%. The alternative hypothesis is that the paired difference between eyes is greater than -10%.

$$H_0: p_c - p_t \leq \delta$$

$$H_a: p_c - p_t > \delta$$

where...

p_t = Test rate of IOP spikes 30 mm Hg or greater

p_c = Control rate of IOP spikes 30 mm Hg or greater

δ = non-inferiority margin: -10%

Success Criteria: If the lower 2-sided 95% confidence interval (equivalent to the 1-sided 97.5% CI) for the difference between the proportions is greater than -10%³.

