20.2 STUDY ENDPOINTS

Primary Endpoints

SAFETY: CUMULATIVE RATE OF IOP SPIKES 30 MMHG OR GREATER MEASURED POSTOPERATIVELY

The cumulative frequency and proportion of eyes with an IOP spike will be reported for both OVD groups for safety population, PP population and sensitivity analysis. For ITT (with data imputation), only the difference between the OVD groups will be reported. The difference in the cumulative IOP spike rate will be analyzed by the McNemar test using a GLIMMIX procedure taking into account the paired data. The GLIMMIX model will model spike as the dependent variable and OVD group as an independent variable and include the SUBJECT = option for the paired eye data. The hypothesis testing of non-inferiority for cumulative percentage of IOP spikes will be tested using a 1-sided, McNemar test at an alpha of 0.025 with a delta of 0.10 (10%). The null hypothesis is that the paired difference between eyes is less than or equal to -10%. The alternative hypothesis is that the paired difference between eyes is greater than -10%.

$$H_0: p_c - p_t \leq \delta$$

$$H_a: p_c - p_t > \delta$$

where...

p_t = Test rate of IOP spikes 30 mm Hg or greater

p_c = Control rate of IOP spikes 30 mm Hg or greater

δ = non-inferiority margin: -10%

Success Criteria: If the lower 2-sided 95% confidence interval (equivalent to the 1-sided 97.5% CI) for the difference between the proportions is greater than -10%².

EFFECTIVENESS: MEAN PERCENT ECC CHANGE PREOPERATIVELY VS. POSTOPERATIVELY

The mean percent change in ECC from preoperative to 3 months postoperative will be reported by descriptive statistics for both OVD groups for safety population, PP

population and sensitivity analysis. For ITT (with data imputation), only the mean difference between the two OVD groups will be reported. The percent change in ECC from preoperative to postoperative is calculated as followed:

$$\text{Percent change in ECC} = (\text{Postop ECC minus Preop ECC})/\text{Preop ECC}$$

The difference in mean percent change in ECC will be analyzed by a paired t-test. The hypothesis testing of non-inferiority for mean percent ECC change will be tested using a 1-sided, paired t-test at an alpha of 0.025 and a delta of 5%. The null hypothesis is that the paired mean difference for mean percent change in ECC is equal to or less than -5%. The alternative hypothesis is that the paired mean difference in percent change between eyes is greater than -5%.

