SAFETY (SF) ANALYSIS

The safety population will consist of all subjects who had any study OVD used and with data available at the time of analysis (i.e., no data imputation). For endpoint analyses using the safety population, if a subject receives only one study OVD then their data will be reported separately since they will not have any between eye difference values. However, if only one eye had a study OVD, then data for that eye will be included in reporting of adverse events and complications. Reporting of cumulative complications (occurring at any time postoperative) will include data from all eyes that had a study OVD.

PER-PROTOCOL (PP) ANALYSIS

The PP population will only include subjects who had surgeries with paired OVDs used, were evaluated within the proper study interval and were without clinically-relevant protocol deviations (deviations that could potentially impact the primary or secondary endpoints for either eye as determined prior to database lock). PP tables will include available data at the time of analysis with no data imputation performed.

Appendix I lists the analysis tables including the endpoints and the populations used to report the results.

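### The primary IOP-spike analysis fixes its target, margin and limit rule, but the McNemar/GLIMMIX route it names does not by itself test that shifted null or yield the deciding limit

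*SAP*

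**What the plan says.** SAP 5.1 and Protocol 20.2 agree. The null is p_c - p_t at or below -10%, where p_c and p_t are the control and test spike rates. The decision rule in SAP 5.1 reads: "Success Criteria: If the lower 2-sided 95% confidence interval (equivalent to the 1-sided 97.5% CI) for the difference between the proportions is greater than" -10%. The test is named in Protocol 20.2: "The hypothesis testing of non-inferiority for cumulative percentage of IOP spikes will be tested using a 1-sided, McNemar test at an alpha of 0.025".

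The computing route in SAP 5.1 is "The difference in the cumulative IOP spike rate will be analyzed by the McNemar test using a GLIMMIX procedure", and the only model detail is this: "The GLIMMIX model will model spike as the dependent variable and OVD group as an independent variable and include the SUBJECT = option". Neither document states a distribution, link, marginal or conditional form, back-transformation or interval method. SAP 2.3, SAP Appendix I and Protocol 20.3 do not fill the gap.

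Elsewhere the SAP works with between-eye differences. In the sensitivity analysis, "a worst-case scenario will be performed with the worst difference score (that favoring the control the most) assigned to the missing data" (SAP 2.1). Safety-set subjects with one study OVD are "reported separately since they will not have any between eye difference values". For ITT, the primary population, imputation applies to subjects who "did not have data available at a specific postoperative visit", and "Data imputation and analysis will be performed using the MI and MIANALYZE procedures". The SAP does not say whether IOP or spike status is imputed, or which estimate and standard error are pooled.

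**The concern.** The criterion needs a confidence limit for a paired difference in proportions. A standard McNemar test compares the two discordant counts against a difference of zero and produces no such limit. A spike model with a subject effect, if fitted as a random-intercept logit, estimates a subject-level log odds ratio. Turned into probabilities at random effect 0, it describes a subject in the middle of the random-effect distribution, not the spike rates that SAP 5.1 defines. A further step is needed and none is written.

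SAP 2.5 requires both primary endpoints to succeed, so this one limit can decide the trial. Two programmers could work from the same text and reach opposite verdicts. Settling the method after unmasking would be open to challenge.

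**Working it through.** **Inputs.** 200 evaluable pairs (SAP 1). Spike rate 30%, correlation 0.5, one-sided alpha 0.025, power 0.80, difference 0.10, n = 195 (SAP 8). Margin -10% (SAP 5.1). The 2x2 tables and the lower spike rates below are illustrations, not document figures. Model fits are Python emulations; SAS was not run.

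**1. The plan's own 195.** At 30% vs 40% with correlation 0.5, the discordant probability is
0.3(0.6) + 0.4(0.7) - 2(0.5)·sqrt(0.3·0.7·0.4·0.6) = 0.46 - 0.2245 = 0.2355.
The exact McNemar test of zero difference then has power 0.801 at n = 195 (0.794 at 192). So 195 reproduces as a zero-null test.

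The non-inferiority version, with equal 30% rates and discordance 2(0.3)(0.7)(1 - 0.5) = 0.21, needs (1.960 + 0.842)²·0.21/0.10² = 165 pairs (Wald), or 177 by the score method. At n = 195 the paired rule has power 0.859 (Wald) or 0.847 (score). The planned N is enough.

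**2. Limits for one table.** Let b = control-only spikes, c = test-only spikes, and n = 200.
- Paired Wald: (b - c)/n - 1.96·sqrt(b + c - (b - c)²/n)/n.
- Paired score (Tango): the value D below (b - c)/n that solves (b - c - nD)/sqrt(n[2q + D(1 - D)]) = 1.96, where q is the test-only probability estimated under p_c - p_t = D.

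For b = 19, c = 23, both = 39 (29% vs 31%), Wald gives -0.02 - 1.96·sqrt(41.92)/200 = -0.02 - 0.0634 = -8.34 points.

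| Method | Lower limit (points) | Verdict |
|---|---|---|
| Paired Wald | -8.34 | pass |
| Identity-link marginal, robust variance | -8.34 | pass |
| Random-intercept logit, averaged over subjects | -8.34 | pass |
| Paired t on differences | -8.40 | pass |
| Paired score (Tango) | -8.53 | pass |
| Random-intercept logit at effect 0, likelihood | -10.18 | fail |
| Same, restricted pseudo-likelihood | -11.37 | fail |

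**3. Where the verdict flips** (42 discordant, 39 both, n = 200):

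| Observed test excess (points) | Wald | Effect 0, likelihood | Effect 0, pseudo-likelihood |
|---|---|---|---|
| 0 | -6.35 | -7.7 | -9.2 |
| 1 | -7.35 | -8.9 | -10.3 |
| 2 | -8.34 | -10.2 | -11.4 |
| 3 | -9.34 | -11.4 | -12.5 |
| 4 | -10.33 | -12.7 | -13.5 |

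The effect-0 reading fails where Wald passes at 2 to 3 points (likelihood) or 1 to 3 points (pseudo-likelihood).

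**4. Operating characteristics at 200 pairs, correlation 0.5.**
- True 30% vs 30%, simulated: effect-0 likelihood passes 71.5% against 85.9% for the paired interval (4,000 trials). Effect-0 pseudo-likelihood passes 58.6% against 85.2% (1,000 trials).
- True 30% vs 40%, at the margin: the two effect-0 versions pass 0.25% and 0.1%. They are over-strict.
- Wald against score, exact enumeration: pass rates 86.8% vs 85.8% at 30/30 and 2.7% vs 2.5% at 30/40. Verdicts differ in 1.0% and 0.3% of trials.

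**5. Below the planned spike rate (assumed rates).**
- For 7/20/11 (9.0% vs 15.5%), Wald is -11.5, score -12.0 and effect-0 pseudo-likelihood -12.4, but effect-0 likelihood is -5.5. Only that last version turns lenient.
- False passes, Wald vs score: 3.6% vs 2.2% at 10/20, and 4.6% vs 2.1% at 5/15. This favours the score interval for observed data.

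**6. Pooled ITT estimate.** Assumptions: 230 pairs, five visits per eye, log-normal IOP, spike correlation 0.53, 30 subjects with missing visits, normal MCMC imputation of IOP, 20 imputations, 2,000 trials. With spike status derived after imputation and (b - c)/n pooled, the mean estimate was -9.9 at a true -10, false non-inferiority 2.6% and power 92.5%.

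**The case against.** The strongest reply is that the harmful reading is not in the plan. SAP 5.1 names no logit link, no random intercept and no evaluation at random effect 0. It does define p_c and p_t as group spike rates and puts success on their difference, so an analyst who reported a contrast at effect 0 would depart from the stated criterion. The text also states the shifted null, and the Protocol synopsis calls the test a McNemar test of non-inferiority. Methods that respect the target agree to about 0.5 point, and a careful statistician would probably choose one of them.

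Most of this stands, and it rules out several stronger conclusions that a reader might draw:
- That GLIMMIX cannot give the limit. It can, by either of the two routes shown above.
- That a literal run of the plan fails good products. The effect-0 reading is one implementation that the text leaves open, not the plan itself.
- That non-significance on a zero-null McNemar test would count as success. The stated criterion excludes this.
- That the gap invites false approval at the planning values, or that N is too small. The figures show neither.

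What does not fall away is that nothing in SAP 5.1 or Protocol 20.2 requires a method aimed at p_c - p_t, and MIANALYZE cannot be programmed without a named estimate and standard error.

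**Conclusion.** The concern holds as missing specification of a deciding analysis, and it should be fixed before unmasking. Target, margin, alpha and rule are sound. The named test does not by itself address the -10% null or produce the limit, and implementations compatible with the wording differ by about 2 to 3 points for a plausible table (-8.34 against -10.18 or -11.37), enough to reverse a co-primary result.

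At 30% and correlation 0.5 the risk falls on the sponsor: for identical products, success drops from about 86% to about 71% or 59% under the effect-0 readings. A lenient error appears only in the likelihood version at spike rates below those planned, which is an assumption. These sizes rest on emulated fits and illustrative tables. The choice between Wald and score matters little at 30% (about 0.2 point) and more at low rates.

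**What to change.** In SAP 5.1, replace the McNemar/GLIMMIX sentences with text such as:

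> p_c - p_t is estimated by the paired difference (b - c)/n, where b = spike in the control eye only and c = spike in the test eye only. In observed-data sets non-inferiority is judged by the lower limit of the two-sided 95% paired score (Tango) interval. For ITT, missing IOP is imputed by eye and visit, spike status is derived in each completed data set, and (b - c)/n and its paired standard error, sqrt(b + c - (b - c)²/n)/n, are pooled with MIANALYZE; the pooled lower 95% limit must exceed -10%. The observed-data score limit is reported beside it, and any disagreement is reported as a non-robust result.

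Related changes:
- Label any GLIMMIX fit supportive and make it marginal (identity link, or averaged over subjects).
- In the sensitivity analysis assign a difference of -1 (spike in the test eye only) for the worst case. First correct SAP 2.1, where the best case is also given the score that favours the control; it should favour the test OVD.
- State whether IOP from unscheduled visits (Protocol 10.9) counts towards a cumulative spike.
- Separately, align SAP 6.3, which names only a McNemar test, with the per-visit non-inferiority test (delta 0.10) in Protocol 20.2. Use the score interval there: with no spikes in 200 pairs the Wald limit collapses to 0, while the score limit is -1.9 points.

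The cost is SAP rewording, a few lines of code and a limit slightly stricter than Wald. No new data and no change in N are needed. Protocol 12 requires FDA and IRB approval for modifications, so change Protocol 20.2 only if the Protocol is being amended anyway; that adds approval time.
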